#### 10.2.1 Overview of Treatment-Emergent Adverse Events

A TEAE overview summary table will be prepared including the number of subjects reporting a TEAE, the percentage of subjects (%) with a TEAE, and the number of events (E) reported, for the following categories:

- Treatment-emergent adverse events
- Treatment-emergent adverse events leading to Deaths
- Treatment-emergent adverse events by intensity
- Serious treatment-emergent adverse events

- Treatment-emergent adverse events leading to withdrawal
- Adverse drug reactions

### **10.2.2 Incidence of Adverse Events**

TEAEs will be summarized in a table by treatment, system organ class (SOC) and preferred term (PT). The table will display the total number of subjects reporting a TEAE, the percentage of subjects (%) with a TEAE, and/or the number of events (E) reported. TEAEs will be presented by SOC sorted alphabetically and PT sorted in decreasing frequency of occurrence.

Summary tables will be prepared for:

- All TEAEs
- TEAEs with an incidence [ $\geq 5\%$ ] of subjects in any treatment group
- TEAEs by causality (related/unrelated)
- TEAEs by intensity

Supporting data listings will be provided for:

- All adverse events
- Serious adverse events
- Adverse events leading to withdrawal.

### **10.3 Safety Laboratory Variables**

Baseline for all laboratory analyses will be the values obtained at the last assessment prior to the first dose of IMP. End of trial will include the last post-baseline observation during the trial.

#### **10.3.1 Summary Statistics**

All chemistry, haematology, haemostasis, and urinalysis laboratory continuous data will be summarized for the baseline and post-baseline evaluations, as well as change from baseline, using descriptive statistics: sample size, mean, median, standard deviation, minimum, and maximum values.

#### **10.3.2 Laboratory Variable Changes Relative to Normal Range**

Changes relative to normal ranges are presented with shift tables with total number of subjects, and number and percent of subjects who experienced a shift.

The following categories for shift tables are defined:

- Low: Values which are below the lower reference range limit;
- Normal: Values which are within the lower and upper reference range;

- High: Values which are above the upper reference range limit.
- Absent: No value for measured variable (for urinalysis only)
- Present: Any value obtained for measured variable (for urinalysis only)

For all haematology, haemostasis and clinical chemistry laboratory variables, shift tables will be prepared to compare baseline values to the worst value at post-baseline (including unscheduled values). More specifically, for haematology, haemostasis and clinical chemistry, tables presenting the changes from *Low* or *Normal* to *High* and from *High* or *Normal* to *Low* will be provided. For urinalysis variables, shift tables will summarize the number (%) of subjects who had “absent” values at baseline and “present” values at post-baseline.

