### 1.2 Scientific Justification for Conducting the Trial

Development of rational therapies for PWS is challenging and there are no approved drug products to treat the complex behavioral symptoms, including hyperphagia. Both children and adults with PWS can be particularly difficult to treat. Shortened attention spans and reduced tolerance for things that are difficult for the individual, combined with expressive language difficulties and slower than normal processing speeds frequently lead to behavioral refusals to complete testing protocols. Therefore, in addition to expert clinical assessment, contributory proxy or caregiver information is necessary for both clinical management and research trials.

The neurohypophyseal hormone, oxytocin, previously thought to only be responsible for milk ejection and uterine contraction during labor, has recently been identified as an important neurotransmitter and key modulator of behavior. Numerous non-clinical and clinical studies, including a small, single-dose, pilot study in PWS subjects suggest that oxytocin delivered via the nasal route will provide therapeutic benefit in treating both hyperphagia and negative behaviors in PWS (6).

Although there may be some positive clinical data, nasal oxytocin does not represent an ideal therapy. Oxytocin is not receptor-selective and, due to its considerable vasopressin V2 receptor activity, it carries the risk of prolonged antidiuresis and hyponatremia (7,8,9). Since some subjects with PWS are known to have polydipsia and low baseline serum sodium levels (10) adding an anti-diuretic increases the risk of serious complications due to hyponatremia. Therefore, a receptor-selective compound would be preferable to avoid these potential side-effects.

Carbetocin (FE 992097) is a selective oxytocin receptor agonist that has 2 amino acid substitutions from the native ligand, oxytocin. Due to the improved selectivity profile and established safety in humans, Ferring has initiated development of this molecule for the treatment of children and adults with PWS.

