### **6.1.1 Screening (Visit 1: Days -7 through 0)**

Prior to or at the Screening Visit, the parent or caregiver must receive a detailed explanation of the trial and must sign the Informed Consent Form after having sufficient time to consider his/her child's participation in the trial. After the parent or caregiver has signed the Informed Consent Form and the subject has signed the Assent Form (if applicable), the following will be collected and/or performed:

- Inclusion/exclusion criteria
- Use of prior/concomitant medication up to 14 days prior to first dose of trial medication
- Parent/caregiver training on completion of HPWSQ-R
- HPWSQ-R followed by HPWSQ-R-C
- CY-BOCS (Symptoms Checklist & Severity Rating Scale)
- Food Domain of Reiss Profile
- Physical examination
- Nasal examination (See scale listed in 7.2.3)
- Medical history and demographic data
- Urine drug and alcohol screen
- Urine pregnancy test for females of childbearing potential
- Vital signs (pulse, respiration rate, blood pressure, and body temperature)
- Height and Weight
- ECG
- Clinical safety laboratory assessment: chemistry, hematology, hemostasis, urinalysis
- Nutritional phase assessment
- Adverse events

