### 7.2.6 Clinical Laboratory Tests

#### Hematology, Hemostasis, Serum Chemistry, and Urinalysis

The following safety laboratory tests will be performed at the times specified in [Table 1](#). A 10-hour overnight fast is required prior to collecting the blood samples. Specific instructions for blood collection will be provided in a laboratory manual to the trial site.

Hematology: red blood cell count, white blood cell count, hematocrit, hemoglobin, platelet count, and differential count.

Hemostasis: prothrombin time, activated partial thromboplastin time, thrombin time, and fibrinogen

Serum chemistry: glucose, blood urea nitrogen, creatinine, potassium, sodium, chloride, calcium, total protein, albumin, total bilirubin, alkaline phosphatase, aspartate aminotransferase, alanine aminotransferase, and gamma glutamyl transferase.

Urinalysis: blood, pH, specific gravity, protein, glucose, urobilinogen, and microscopic if positive for blood or protein.

The investigator is to review laboratory results for abnormalities and clinical significance.

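### The urinalysis shift rule in SAP 10.3.2 cannot register any change in pH or specific gravity

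*Combined protocol and SAP*

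**What the plan says.** SAP 10.3.2 introduces its shift tables as a display of movement against the reference range. It defines five categories. Low, Normal and High are set by the reference limits. The other two apply to urinalysis alone: "Absent: No value for measured variable (for urinalysis only" and "Present: Any value obtained for measured variable (for urinalysis only".

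The section then says which tables will be made. Haematology, haemostasis and clinical chemistry get Low/Normal/High shifts from baseline to the worst post-baseline value, unscheduled values included. Urinalysis gets something different: "For urinalysis variables, shift tables will summarize the number (%) of subjects who had “absent” values at baseline and “present” values at post-baseline".

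Protocol 7.2.6 gives the panel: "Urinalysis: blood, pH, specific gravity, protein, glucose, urobilinogen, and microscopic if positive for blood or protein". Urinalysis is part of the screening visit (Protocol 6.1.1) and is repeated at Visits 3 and 4 (Protocol Table 1). SAP 10.3 fixes the reference point: "Baseline for all laboratory analyses will be the values obtained at the last assessment prior to the first dose of IMP".

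**The concern.** A shift table shows how many subjects in each arm were in range before treatment and out of range afterwards. For urinalysis the SAP sets the reference range aside and asks instead whether a value exists. That cannot work for pH and specific gravity, which have a value in every sample. Their rows would be empty for reasons of coding, and a reader could take the empty rows as a finding.

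Specific gravity is also the only measure of urine concentration in the panel. Protocol 1.2 discusses water balance when it explains why oxytocin is not ideal: "due to its considerable vasopressin V2 receptor activity, it carries the risk of prolonged antidiuresis and hyponatremia". A display that cannot show a change in urine concentration is therefore not a purely cosmetic matter. SAP 10.1 plans no formal testing of safety data, so the descriptive tables and listings are the safety evaluation.

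**Working it through.** The plan states no figure on this point, so there is nothing to reproduce. The check is to apply the stated rule.

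**Inputs.** Category definitions and the tabulated shift: SAP 10.3.2. Panel: Protocol 7.2.6, six routine variables (blood, pH, specific gravity, protein, glucose, urobilinogen), with microscopy only when blood or protein is positive. Baseline: last pre-dose assessment (SAP 10.3), which on the planned schedule is the screening sample. Arm size: about 19 randomised per arm (SAP 3.2).

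**Rule.** Subject *i* counts as a shift if baseline is Absent and post-baseline is Present. For pH or specific gravity:

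| Baseline sample | Post-baseline sample | Categories | Counted as a shift? |
|---|---|---|---|
| taken | taken, in range | Present, Present | no |
| taken | taken, out of range | Present, Present | no |
| missing | taken, in or out of range | Absent, Present | yes |

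The first two rows are indistinguishable, so the count is 0 among all subjects with a baseline sample, in each arm. This affects 2 of the 6 routine variables. The third row is a second fault of the literal wording: one missing baseline gives one false shift.

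**A more generous reading.** Suppose Absent and Present were meant as dipstick negative and positive. That suits blood, protein and glucose. It does not help pH or specific gravity, which have no negative result, so their count is still zero.

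**Other displays.**
- SAP 10.3.3 (markedly abnormal values) depends on Appendix 1, which lists haematology, haemostasis and chemistry only. It gives no count for pH or specific gravity.
- SAP 10.3.1 summarises continuous urinalysis data at baseline, post-baseline and as change, with mean, median, standard deviation, minimum and maximum. It does not say how many subjects moved out of range.
- SAP 10.3.4 lists values by treatment, subject and test and identifies those out of range. The information is there, but not tabulated.

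**Illustration of what the table would leave out.** These inputs are assumptions and are not in the documents: specific gravity normally distributed with mean 1.020 and SD 0.006, upper limit 1.030, 19 subjects in an arm, one post-baseline value independent of baseline. Expected Normal-to-High shifts, ignoring a lower limit, are 19 × P(baseline ≤ 1.030) × P(post-baseline > 1.030). The first probability is Φ(0.010/0.006) = Φ(1.67) = 0.952.

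| Upward drift on treatment | P(post-baseline > 1.030) | Expected Normal-to-High shifts | Count under the SAP rule |
|---|---|---|---|
| 0 | 0.048 | 19 × 0.952 × 0.048 ≈ 0.9 | 0 |
| +0.005 | 0.202 | 19 × 0.952 × 0.202 ≈ 3.7 | 0 |
| +0.010 | 0.500 | 19 × 0.952 × 0.500 ≈ 9.0 | 0 |

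A simulation with the same inputs gave means of 0.85, 3.66 and 9.01, and 0 throughout under the SAP rule. The drifts show a range; they do not predict a drug effect.

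**The case against.** The sponsor can fairly say that little is lost. The serious complication that Protocol 1.2 has in mind is hyponatremia, and serum sodium is followed directly. A screening value below 135 mmol/L excludes the subject. Sodium is in the chemistry panel at Visits 1, 3 and 4. It has a baseline-to-worst shift table and by-arm markedly abnormal limits (≤ 130 and ≥ 150 mmol/L). For specific gravity itself, the maximum in SAP 10.3.1 would show an extreme value, and with about 19 subjects per arm the flagged listing can be counted by hand. A laboratory abnormality judged clinically significant is also an adverse event (Protocol 8.1) and would enter the adverse event tables by arm. All of this stands and limits the consequence. It does not make the shift rule work for the two variables.

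A reader might infer three stronger points, which the documents do not support.

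- **That an antidiuretic risk of carbetocin goes unmonitored.** Protocol 1.2 assigns that risk to oxytocin and presents carbetocin's receptor selectivity as the way to avoid it. The documents do not describe it as a risk of carbetocin or of the class. The link from specific gravity to antidiuresis is general physiology and is not stated in them either.
- **That all six routine urinalysis rows are empty.** This needs a negative dipstick result to count as a value obtained. In a section about reference ranges, the natural sense for blood, protein, glucose and urobilinogen is not detected versus detected. The wording there should be clearer, but a zero count does not follow.
- **That a row of 0% against 0% will be printed and taken as evidence of no effect.** The table shells are in a separate document (SAP 14), so whether pH and specific gravity appear in that table cannot be seen.

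**Conclusion.** The point holds for pH and specific gravity. Under SAP 10.3.2 neither can register a shift for any subject with a baseline sample, in either arm, on the literal or the generous reading of Absent and Present. No other planned laboratory table counts by arm the subjects who leave the reference range on these variables. The conclusion rests on one fact outside the documents, that both tests return a number on every sample. The false shift from a missing baseline rests on the literal wording and arises only if a scheduled screening sample is missing.

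The size is modest. No endpoint test or decision rule depends on this table, the values are still summarised and listed, and sodium is well covered. It is a specification error worth correcting because the rule defeats the section's own purpose and the correction is cheap.

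**What to change.** In SAP 10.3.2:

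1. Add pH and specific gravity to the Low/Normal/High shift tables, comparing baseline with the worst post-baseline value against the laboratory reference range.
2. Limit Absent/Present to blood, protein, glucose and urobilinogen. Define Absent as a result reported negative or normal, and Present as a result reported positive or above normal.
3. Show a missing sample as missing, never as Absent.

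The cost is a short change to the SAP text and one table shell. No new data are needed: the samples are already scheduled, and SAP 10.3.4 already requires out-of-range values to be identified, which presupposes reference ranges. The change should be made before unblinding.

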#### **10.3.3 Markedly Abnormal Changes**

A summary table will be prepared that displays for each laboratory variable the number and percentage of subjects in each treatment group with normal baseline values who had at least one pre-specified markedly abnormal value anytime during the treatment period. Pre-specified markedly abnormal criteria for laboratory tests are given in Appendix 1.

#### **10.3.4 Data Listings**

Clinical safety laboratory values will be listed by treatment, subject and test. All values outside the normal range will be identified.

Subjects with any markedly abnormal changes at any time-point will be also listed with all values of the corresponding laboratory tests. The laboratory values with markedly abnormal changes will be flagged out.

### **10.4 Vital Signs and ECG**

#### **10.4.1 Vital Signs**

Baseline for all vital signs (blood pressure, pulse, body temperature, and respiration rate) analyses will be the values obtained at the last assessment prior to the first dose of IMP. End of trial will include the last post-baseline observation during the trial.

##### **10.4.1.1 Summary Statistics**

All vital signs data will be summarized for the baseline and post-baseline evaluations, as well as change from baseline, using descriptive statistics: sample size, mean, median, standard deviation, minimum, and maximum values.

##### **10.4.1.2 Markedly Abnormal Changes**

A summary table will be prepared that displays for each vital signs parameter the number and percentage of subjects in each treatment group with normal baseline values who had one or more

pre-specified markedly abnormal treatment-emergent values, according to the definition in Appendix 1. The markedly abnormal criteria will be used to define normal baseline as well.

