### **7.2.4 Height, Weight and Vital Signs**

Height and weight will be measured at Visit 1 and Visit 4.

Pulse, respiration rate, blood pressure, and body temperature will be measured at each visit (or at early termination) under resting conditions while the subject is seated. All blood pressure measurements should be made using the same arm while the subject is in supine position after resting for 3 minutes, and prior to any scheduled blood draws. At Visit 2 and Visit 3 - vital signs will be monitored prior to and after IMP dosing at 30-minute intervals for 2 hours after each dose.

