### **Safety endpoints**

- Frequency, severity and seriousness of adverse events
- Clinically significant changes in vital signs
- Clinically significant findings during physical and laboratory assessments
- Physical examinations, including focused nasal examinations and nasal irritation, graded according to the following scale:

Grade 0 = no abnormal findings

Grade 1A = focal nasal mucosal inflammation, erythema, or hyperemia

Grade 1B = superficial nasal mucosal erosion

Grade 2 = moderate nasal mucosal erosion

Grade 3 = nasal mucosal ulceration

Grade 4 = nasal septum perforation

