**Markedly abnormal blood pressure levels for BOYS by age**

Age (years)	Unit	SBP Lower limit ( $\leq$ )	SBP Upper limit ( $\geq$ )	DBP Lower limit ( $\leq$ )	DBP Upper limit ( $\geq$ )
10 years $\leq$ x < 11 years	mmHg	77	127	34	88
11 years $\leq$ x < 12 years	mmHg	79	129	35	89
12 years $\leq$ x < 13 years	mmHg	81	131	35	89
13 years $\leq$ x < 14 years	mmHg	84	134	36	90
14 years $\leq$ x < 15 years	mmHg	86	136	36	90
15 years $\leq$ x < 16 years	mmHg	89	139	37	91
16 years $\leq$ x < 17 years	mmHg	92	141	39	93
17 years $\leq$ x < 18 years	mmHg	94	144	41	95
18 years $\leq$ x < 19 years	mmHg	94	144	41	95

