**Markedly abnormal blood pressure levels for GIRLS by age**

Age (years)	Unit	SBP Lower limit (<math>\leq</math>)	SBP Upper limit (<math>\geq</math>)	DBP Lower limit (<math>\leq</math>)	DBP Upper limit (<math>\geq</math>)
10 years $\leq x < 11$ years	mmHg	78	126	35	86
11 years $\leq x < 12$ years	mmHg	80	128	36	87
12 years $\leq x < 13$ years	mmHg	81	130	37	88
13 years $\leq x < 14$ years	mmHg	83	132	38	89
14 years $\leq x < 15$ years	mmHg	85	134	39	90
15 years $\leq x < 16$ years	mmHg	86	135	40	91
16 years $\leq x < 17$ years	mmHg	87	136	41	92
17 years $\leq x < 18$ years	mmHg	87	136	41	92
18 years $\leq x < 19$ years	mmHg	87	136	41	92

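### The vital-sign flag uses absolute limits and change is taken only from the reading before the first dose, so acute change after on-site doses 2 to 6 has no pre-specified comparison by arm

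*Combined protocol and SAP*

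**What the plan says.** **Endpoint.** Protocol 2.2 and SAP 2.2 both list "Clinically significant changes in vital signs" as a safety endpoint.

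**Measurement.** Protocol 7.2.4 states that at Visits 2 and 3 "vital signs will be monitored prior to and after IMP dosing at 30-minute intervals for 2 hours after each dose". Dosing is three times a day, and both days are dosed on site.

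**Reference value.** SAP 10.4.1 sets the baseline: for all vital-sign parameters, "analyses will be the values obtained at the last assessment prior to the first dose of IMP". SAP 10.4.1.1 summarises baseline and post-baseline values "as well as change from baseline, using descriptive statistics: sample size, mean, median, standard deviation, minimum, and maximum values".

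**Flag.** SAP 10.4.1.2 is headed as being about changes. It counts subjects with a normal baseline who had one or more "pre-specified markedly abnormal treatment-emergent values, according to the definition in Appendix 1", and adds: "The markedly abnormal criteria will be used to define normal baseline as well". Appendix 1 Table 2 gives lower and upper limits, for example under "Markedly abnormal blood pressure levels for BOYS by age" and "Markedly abnormal blood pressure levels for GIRLS by age". It has no column for size of change. The flagged listing in SAP 10.4.1.3 uses the same criteria.

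**The concern.** The endpoint is worded as change, and the readings around each dose would let acute post-dose change be measured six times per subject. The analysis uses that structure only for the first dose, where the planned baseline is normally that dose's own pre-dose reading. For the other five doses, the pre-dose reading never serves as a reference. The acute effect of the dose is then combined with whatever moved that subject's level between the first morning and the dose in question.

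The flag does not fill this gap, because it responds to where a reading lies and not to how far it has moved. What is at stake is a clear, pre-specified comparison between carbetocin and placebo of blood pressure and pulse in the two hours after dosing. The trial plans about 19 subjects per arm and has no data monitoring committee, so individual excursions carry much of the safety information.

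**Working it through.** The plan states no figure of its own here, so there is none to reproduce. Three checks follow.

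**1. How much of the on-site data has a same-dose reference**

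Inputs: three doses a day on two on-site days; one pre-dose reading and four post-dose readings (30, 60, 90 and 120 minutes) per dose.

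- Doses: 2 × 3 = 6.
- Post-dose readings per subject: 6 × 4 = 24.
- Post-dose readings at doses 2 to 6: 5 × 4 = 20.

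So 20 of 24 post-dose readings are compared only with a value from an earlier dosing occasion. Under the protocol's dosing windows (morning 06:00 to 09:00, evening 16:30 to 18:00), the Day 2 evening dose falls 31.5 hours (09:00 to 16:30 the next day) to 36 hours (06:00 to 18:00 the next day) after the Day 1 morning dose.

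For dose *k*, within-dose change = (post-dose − first baseline) − (pre-dose *k* − first baseline). The SAP analyses the first bracket and never subtracts the second.

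**2. Largest within-dose fall that the flag cannot see**

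The limits are inclusive: a value is flagged at or below the lower limit L, or at or above the upper limit U. In whole units, the widest unflagged fall is (U − 1) − (L + 1) = U − L − 2.

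| Stratum | SBP limits L / U | Unflagged SBP path | Fall (mmHg) |
|---|---|---|---|
| Boys, 10 years | 77 / 127 | 126 to 78 | 48 |
| Boys, 16 years | 92 / 141 | 140 to 93 | 47 |
| Boys, 17 and 18 years | 94 / 144 | 143 to 95 | 48 |
| Girls, 10 years | 78 / 126 | 125 to 79 | 46 |
| Girls, 12 years | 81 / 130 | 129 to 82 | 47 |
| Girls, 16 to 18 years | 87 / 136 | 135 to 88 | 47 |

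Over all 18 age and sex rows, the systolic maximum is 48 mmHg for boys (47 at age 16) and 46 mmHg (ages 10 and 11) or 47 mmHg (ages 12 to 18) for girls. The diastolic maximum is 52 mmHg for boys (for example 88 − 34 − 2) and 49 mmHg for girls (86 − 35 − 2). For pulse it is 46 beats per minute in every row (for example 94 − 46 − 2, a path from 47 to 93 or the reverse).

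**3. The same question from a mid-range starting value**

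The documents give no typical blood pressure, so a pre-dose SBP of 110 mmHg is an assumption for illustration. The largest unflagged fall is 110 − (L + 1):

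- Boy of 10: 110 − 78 = 32 mmHg.
- Girl of 10: 110 − 79 = 31 mmHg.
- Girl of 17: 110 − 88 = 22 mmHg.
- Boy of 17: 110 − 95 = 15 mmHg.

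The size of fall needed to trigger the flag therefore depends on age, sex and starting level.

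**The case against.** Several points on the other side stand.

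- **A large fall need not go uncounted.** A reader might infer that it would appear in no count. The documents do not support that. Under Protocol 8.1, a vital sign that the investigator judges clinically significant is an adverse event, and SAP 10.2 tabulates treatment-emergent events by arm. The readings are taken under staff observation. This route relies on judgement, however, and has no common numerical comparison.
- **Individual extremes are partly visible.** Minimum and maximum change from the first-dose baseline are tabulated and all values are listed. If the summary is shown by timepoint, a mean within-dose change could be found by subtracting two means when data are complete, but its spread and extremes could not. SAP 10.4.1.1 does not mention timepoints, and Protocol 9.8.4 says only treatment and visit. SAP 10.5.1, by contrast, names timepoints for the nasal examination.
- **The first-dose baseline is not wrong.** It is the only on-site reference free of drug. Pre-dose readings for doses 2 to 6 follow earlier exposure, and used alone they could hide a sustained or cumulative effect. Randomisation and a common schedule also mean that time-of-day drift does not bias the difference in means between arms. It still adds noise to that comparison and obscures each subject's own response.
- **The flag is not blind to all change.** It needs a normal baseline followed by an abnormal value, which is a shift. What it lacks is a criterion for size of change.
- **The 46 to 48 mmHg figure is a corner case.** It needs a start one unit inside one limit and a lowest value one unit inside the other.
- **A round threshold is not the obvious remedy.** The documents support none. As an illustration, assume 20 mmHg and a standard deviation of 8 to 10 mmHg for a within-dose difference under no effect. The two-sided normal tail is 0.0124 (20/8 = 2.5) to 0.0455 (20/10 = 2). Over 24 independent readings, 1 − (1 − 0.0124)^24 = 26% and 1 − (1 − 0.0455)^24 = 67% of subjects would meet it by chance. Independence makes these upper bounds.

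The documents describe the 30-minute readings as monitoring and do not say that they were meant for an analysis of acute change. The table shells are in a separate document, so by-dose displays may be planned there.

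**Conclusion.** The point holds as a gap in the planned analysis. The safety endpoint concerns change, yet the SAP has no subject-level rule based on size of change and no analysis of within-dose change for five of the six on-site doses. The available routes (investigator judgement, listings, and extremes measured from the first baseline) do not amount to a pre-specified comparison of acute post-dose change by arm.

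The gap covers 20 of 24 post-dose readings per subject. The flag's blind range reaches 46 to 48 mmHg systolic at the extreme, and 15 to 32 mmHg from a starting value of 110 mmHg in the strata checked. These figures assume readings in whole units and all three doses given on site on both days. They describe what the rule can miss and do not predict that such falls will occur.

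No data are lost, so this is an inexpensive improvement and not a flaw that invalidates the safety analysis.

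**What to change.** - **SAP 10.4.1:** keep the baseline before the first dose as the reference for sustained effects.
- **SAP 10.4.1.1:** for Visits 2 and 3, also summarise change from the same dose's pre-dose reading, by arm, dose and timepoint.
- **By-subject extremes:** add a summary by arm, with a listing, of each subject's largest post-dose fall and largest post-dose rise in SBP, DBP and pulse, measured from the same dose's pre-dose reading.
- **SAP 10.4.1.2 and Appendix 1 Table 2:** if a numerical change criterion is wanted, the sponsor's clinical team should choose it and fix it before unblinding. None is proposed here.
- **Wording:** say in 10.4.1.2 that the existing count identifies levels outside limits after a normal baseline, so that its heading is not read as an analysis of size of change.

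The cost is SAP text and two or three more descriptive tables. All readings are already scheduled. The downside is more values to review in both arms.
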